The proposed project takes place in two parts: part one builds upon the evidence base of the effectiveness of culturally tailored CHW interventions and proposes to replicate and scale a CHW intervention. A critical need exists to tailor, translate, and disseminate evidence-based CHW interventions to maximize impact in ameliorating co-morbid CVD disparities. Part two describes the variation of cardiovascular disease risk across South Asian populations in the US derived from electronic health records. Our study takes a first step towards filling this gap in the literature, by characterizing the burden of disease among two South Asian communities. This project will facilitate bidirectional collaboration by building this data set across two sites in the United States. This will complement ongoing work by the investigative team to replicate an efficacious intervention program delivered in NYC in Atlanta.

B. Study aims

Specific Aim 1: Provide research training, technical assistance, and capacity-building to community and clinical sites in Georgia for implementation of culturally tailored, evidenced-based CHW programs to improve HTN and diabetes management for South Asians.

Specific Aim 2: Use a multi-theoretical framework to test the effectiveness of a CHW-led intervention compared to usual care among South Asian individuals with diabetes and uncontrolled HTN in Atlanta.

Specific Aim 3: Apply RE-AIM and CFIR frameworks to delineate factors influencing reach, appropriateness, fidelity, adoption, and maintenance of the intervention within clinical and community settings to optimize intervention replication.

Sub-Aim3a: Serve as a national information and dissemination resource in the adaptation of evidence-based strategies to reduce geographic disparities in HTN and diabetes across Asian American groups.

B. Study Outcomes

Phase 1: See below: this is the planning and technical assistant phase of the proposal.

Phase 2: The primary outcome of interest is proportion of patients that achieve BP control, defined as less than or equal to 130/80 mmHg, at 6 months. The secondary outcomes of interest include changes in HbA1c, SBP and DBP, and BMI at 6 months.

Phase 3: The outcomes for the provider surveys, informant surveys, and EHR will be descriptive data to inform with to facilitate the development of intervention strategies within the larger healthcare system

III. STUDY DESIGN

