Practices that express interest in participating in the CHW intervention will sign a Memorandum of Understanding (MOU) that outlines the nature of the evaluation and the uses of any data collected, including:

Intervention Components

A minimum set of proposed intervention components will be implemented including:

- 5 group-based health education sessions on hypertension and diabetes management
- Provision of culturally and linguistically tailored health information and resources

- Two one-on-one in-person meetings that can be at the participants home or at the participants clinical site and 7 follow-up phone calls to engage in goal-setting activities regarding changes to health behaviors, medication adherence, or other issues related to diabetes prevention as identified jointly by patient and CHW.
- Participants will develop with the CHW and receive a copy of their long-term and short-term Participant Action Plan.
- Referrals to other services available in the community (i.e. exercise classes, social services, mental health, tobacco cessation, etc.

CHW Curriculum

Participants enrolled in the CHW intervention will receive group-based health education sessions:

Curriculum Session Title & Content	Tailored cultural components

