During the study period, the research team will be performing a retrospective chart review of South Asians, using surnames to identify patients of South Asian origin. We will submit a waiver of consent to obtain these records.

VII. DATA COLLECTION AND ANALYSES

A. PHASE 2: Data collection and implementation of the CHW intervention (recruitment, consenting, CHW led education sessions) will be led by Emory University. All participants will attend Session 1. Everyone who attends will receive a unique study identifier that will associate a specific study number with the participant. This information will then be downloaded onto the NYU servers into R statistical software for randomization. We will use stratified randomization by age and gender to assign patients to intervention or control arms.. The table necessary to link patient identifiers and the study ID will be maintained by the Emory-based study coordinator to ensure that patient confidentiality is maintained.

Treatment Participants

The study ID will be used for all implementation activities and reporting on CRFs. Thus, patients who are observed more than once will have the same study ID in each extract, which is necessary for the planned analyses. Study data will be collected in the form of a survey at baseline and at endpoint. Follow up calls and visits will also be recorded in REDCap, or paper-based CRFs and kept in locked boxes until transport back to the Emory Dunwoody offices for input into REDCap and secure storage.

A random sample (n=50) of less engaged and more engaged previously enrolled treatment group participants of the CHW intervention will receive an invitation to participate in the focus group. This will be a one-time anonymous audio-recording with no follow-up; no names or identifying information will be collected at the time of the focus group.

The focus group will be completed in-person or virtually via Zoom (Emory University has HIPAA compliant Zoom accounts which have been institutionally approved for telemedicine, see supporting documentation) to accommodate the current COVID-19 situation. The method (face-to-face vs. virtual) will be determined at the discretion and preference of the participants, while following institutional regulations for COVID-19. Recordings will only include audio (not video).

Control Participants

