The control participants will all participate in baseline and endpoint surveys with the CHWs. They will also complete a Session 1 educational session. Control participants will not be contacted during the rest of

the 6-month intervention phase and will be contacted by the clinic staff only when the intervention is complete among treatment participants. Those in the first wave will be offered the intervention in the second wave. The second wave control group will be offered educational sessions as a point of service and not as part of research (i.e., wait-listed control study design).

B1. Data Analysis and Monitoring

The NYU site will lead the data analysis portion of the study, with input and feedback from Emory research staff.

Specific Aim 2 Analysis.

Specific Aim 2: To compare the effect of the intervention with usual care on achieving BP control among individuals with diabetes. The primary outcome will be the proportion of eligible patients at a practice site to achieve BP control (130/80 mmHg) six months following the index office visit. *Hypothesis:*

Individuals receiving care during the implementation of the intervention will be more likely achieve BP control six months following the index office visit than individuals receiving care as usual. The primary outcome of interest is the proportion of patients who achieve BP control. The secondary outcomes of interest include changes in HbA1c, SBP and DBP, and BMI at 6 months. For analyses of both primary and secondary outcomes, a logistic regression model will be used to estimate the CHW effect on outcomes (see equation 1):

$$(1) \quad \text{logodds}[P(Y_{ij})] = \beta_0 + \gamma_j + \beta_1 H$$

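### Aim 2 names usual care as the comparator, but every control also attends Session 1, so the trial estimates what the rest of the programme adds to that session

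*Combined protocol and SAP*

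**What the plan says.** **Comparator as stated.** Specific Aim 2 (II.B) is to "test the effectiveness of a CHW-led intervention compared to usual care". The Specific Aim 2 Analysis (VII.B1) restates the purpose: "To compare the effect of the intervention with usual care on achieving BP control among individuals with diabetes". Its hypothesis is that BP control will be more likely under the intervention "six months following the index office visit than individuals receiving care as usual". It describes the primary outcome as "the proportion of eligible patients at a practice site to achieve BP control".

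**Comparator as delivered.** VII.A says "All participants will attend Session 1". Those who attend are given a study identifier, and the section continues: "This information will then be downloaded onto the NYU servers into R statistical software for randomization". Under Control Participants it adds: "They will also complete a Session 1 educational session". After that, controls have no contact for the remainder of the six-month phase.

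**What Session 1 is.** IV.A1 lists "5 group-based health education sessions on hypertension and diabetes management" among the minimum intervention components. The curriculum gives Session 1 as the hypertension and diabetes overview, and its content includes dietary salt and blood pressure. VI.A places it in Month 1 of the intervention period.

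**Waves.** VI.A and VII.A allow first-wave controls to receive the intervention in the second wave. Second-wave controls are offered sessions outside the research. In VII.B1, the treatment indicator in equation (1) is set by randomised arm, and the control term refers to the first six months.

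**The concern.** The comparator named in the aim and hypothesis is the one that will be carried into the report. If both arms receive Session 1, any effect of that session cancels from the randomised difference. A reader told that the result is programme versus usual care would take it for the effect of adopting the whole programme, which matters because the study's purpose is to replicate and scale it. If Session 1 improves BP control, the reported difference understates that effect. A null result would be open to the wrong reading that the programme does no better than usual care.

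The second issue is smaller. A first-wave control who enters wave 2 could generate a second six-month record, this time while treated. The plan does not say in terms whether such a record enters the primary model.

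**Working it through.** **1. The plan's own sample size.** VII.B2 assumes 15% control and 35% treatment BP control, two-sided 0.05, more than 80% power and 10% loss, giving 162. With pooled variance:

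- n per arm = [1.960 × √(2 × 0.25 × 0.75) + 0.842 × √(0.15 × 0.85 + 0.35 × 0.65)]² / 0.20² ≈ 72.4, so 73.
- Allowing for loss: 73 × 1.1 = 80.3, so 81 per arm (162); or 73 / 0.9 = 81.1, so 82 per arm (164).
- Power at 81 × 0.9 = 72.9 evaluable per arm is 80.3%.

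The figure reproduces. The present point does not depend on it.

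**2. How much of the programme is randomised.** Inputs are the components in IV.A1 and the monthly schedule in VI.A.

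- Calls, Months 1 to 5: 1 + 1 + 2 + 1 + 2 = 7, agreeing with IV.A1.
- Scheduled contacts: 5 sessions + 2 in-person meetings + 7 calls = 14.
- Contacts beyond Session 1: 4 + 2 + 7 = 13, and 13/14 = 93%.
- Session 1 alone: 1/5 = 20% of group sessions, 1/14 = 7% of contacts.
- Participants planned without Session 1, on VII.A's wording: 652 − 652 = 0.

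These are shares of contact, not of effect.

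**3. What is estimated.** Write C for usual care alone, S for usual care plus Session 1, and P for the full programme, each as the log odds of BP control. Then

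P − C = (P − S) + (S − C).

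The randomised arms identify P − S. No arm identifies S − C. A null P − S leaves P − C equal to S − C, which is unknown. A positive P − S implies a positive P − C provided that S − C is not negative.

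**4. Validity of the test.** VII.A puts Session 1 before randomisation and gives it to everyone. It is common to both arms, so it does not bias P − S.

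**5. VI.A against VII.A.** Under CHW Screening Period, VI.A says that controls have no contact while the intervention runs and are approached only once it has finished for treated participants. The same section makes Session 1 part of Month 1 of that intervention. VII.A has controls attend Session 1 and stops contact only afterwards. Read literally, these cannot both hold.

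**6. Second-wave records.** VII.B1 takes the outcome at the end of the six months, sets the treatment indicator by randomised arm and ties the control term to the first six months. That implies one record per person, from the first randomised period. No sentence says so, and equation (1) has only an intercept, a site effect and the treatment term. If a re-enrolled first-wave control supplied a second record, keeping the original arm code would count a treated outcome as control and pull the difference towards zero if the intervention works. Recoding it as treated would put the same person in both arms with no patient or wave term.

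**The case against.** The strongest reply is that this is a label. Controls' attendance at Session 1 is disclosed, the tested contrast is already arm as randomised, Session 1 is one contact in 14, and a positive result would still support superiority over usual care if Session 1 does no harm. Most of that stands: the test needs no change, and a positive finding keeps its direction. What remains is the size of the effect and the reading of a null result, and both depend on which comparator is named.

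A reader might infer several stronger things that the documents do not support:

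- *That the comparison is biased, or can say nothing about usual care.* Session 1 is common to both arms, and steps 3 and 4 above show what survives.
- *That second-wave control data are free to enter the model.* VII.B1 points to the first randomised six months. Outcomes of people newly randomised to control in wave 2 are proper randomised data and should stay. Only a second record from a re-enrolled first-wave control is in question.
- *That VII.A's remark about patients observed more than once anticipates such records.* It stands under Treatment Participants, and the baseline and endpoint surveys explain it.
- *That the analysis is a before-after or matched comparison.* III.B1 calls pre-intervention time the comparison group, but its next sentence describes randomised wait-list controls. VII.B3 says matched, but VII.B1 and VII.B2 use randomised arms. These are loose words that leave the planned model unchanged.

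**Conclusion.** The point holds as a mismatch between the stated and the delivered comparator. On VII.A's wording, none of the 652 planned participants has usual care without Session 1, and the randomised contrast covers 13 of 14 scheduled contacts. The test is valid for the effect beyond Session 1. It does not give the size of the full programme's effect against usual care, and a null result would not show that the programme is no better than usual care. The documents report no effect for Session 1 alone, so neither the size of any understatement nor any loss of power can be stated.

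This rests on VII.A describing what will happen. VI.A's no-contact statement conflicts with it. If the reconciled text had controls skip Session 1, the usual-care label would stand and VII.A would have to change.

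The second-wave point is a missing sentence. The planned model implies the right rule but does not state it.

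**What to change.** 1. In Specific Aim 2 (II.B) and the Specific Aim 2 Analysis (VII.B1), restate the aim, hypothesis and planned conclusion as CHW programme versus usual care plus Session 1. Define the outcome among randomised participants, in place of eligible patients at a practice site, to match the population on which equation (1) is defined. Reconcile the no-contact statement in VI.A with VII.A at the same time.

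2. After equation (1), add: *Each participant contributes one 6-month outcome, in the arm and wave of first randomisation; later records from re-enrolled first-wave controls do not enter the primary model. Outcomes of participants newly randomised in wave 2, controls included, are retained.*

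3. As tidying only, align the pre-intervention-time and stepped-wedge wording in III.B1, and the word matched in VII.B3, with the concurrent randomised comparison.

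The cost is protocol and analysis wording, with no change to the sample size or the form of the model. The downside is that the claim narrows to the effect beyond one education session, and repeat data from former controls add nothing to the primary test.

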A randomized control design will be used to test the efficacy of the CHW intervention to improve HTN control among South Asian individuals with diabetes in Atlanta. The intervention will recruit participants from three clinical sites in Atlanta, GA: 1) The Emory Family Medicine Clinic is located in North Atlanta and serves approximately 1,200 unique South Asian patients annually; 2) Grady Clinic at Brookhaven is a safety net county clinic that sees a high volume of low-income South Asians (approximately 6,000 per year; 3). The Shifa Free Clinic is a community-based free clinic coordinated by the Islamic Circle of North America, Atlanta branch, to serve uninsured and under-insured South Asians in Georgia.. On average, they see 200 unique South Asian patients per month at each site. Both Emory Family Medicine Clinic and Grady Clinic utilize EHR systems which will be used to generate lists of eligible patients for the intervention. Shifa Clinic is currently transitioning to an EHR system, thus patient data will be electronically accessible for patient recruitment and follow-up outcome data. Each of the sites has expressed interest and commitment to participating in the study. The community centers will not be engaged in research, all consenting and procedures will be completed by Emory study staff.

We also anticipate enrolling participants from community-based recruitment with the CHWs referring participants that they meet at South Asian community events and advertising the study. The proposed research design is a modified stepped wedge design, whereby 2 groups will implement the intervention in phases. The time prior to the intervention will serve as the comparison group. Enrolled patients will be randomized to treatment (Group A) and wait-list control (Group B) groups within each site.

There are five primary research groups for this study: 1) 326 treatment participants who will receive the CHW intervention; 2) 326 control participants who may receive the CHW intervention as a point of service at a later point; 3) 10 subjects who will participate in provider surveys; 4) 25 subjects who will participate in qualitative key informant interviews; 5) a retrospective EHR review of characteristics of South Asians seen at Emory Healthcare and NYU hospital system between 2014 and 2019; and 6) 50 subjects who will participate in focus groups.

B2. CHW Component:

1. Data collection and consenting with treatment participants

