Type 2 Diabetes Mellitus	E11.00, E11.01, E11.21, E11.22, E11.29, E11.311, E11.319, E11.321, E11.329, E11.331, E11.339, E11.341, E11.349, E11.351, E11.359, E11.36, E11.39, E11.40-E11.44, E11.49, E11.51, E11.52, E11.59, E11.610, E11.618, E11.620-E11.622, E11.628, E11.630, E11.638, E11.641, E11.649, E11.65, E11.69, E11.8, E11.9, E13.00,	Therapeutic class of Antihyperglycemic, excluding medication names of Metformin and Acarbose	A1C: 4548-4, 7426-0, 4549-2, 17856-6, 59261-8, 71875-9, 62388-4, 4637-5, 55454-3, 41995-2, 17855-8

	E13.01, E13.10, E13.11, E13.21, E13.22, E13.29, E13.311, E13.319, E13.321, E13.329, E13.331, E13.339, E13.341, E13.349, E13.351, E13.359, E13.36, E13.39, E13.40-E13.44, E13.49, E13.51, E13.52, E13.59, E13.610, E13.618, E13.620, E13.621, E13.622, E13.628, E13.630, E13.638, E13.641, E13.649, E13.65, E13.69, E13.8, E13.9		
--	---	--	--

V. STUDY ENROLLMENT

A. Characteristics of the research population

The overall number of subjects expected to participate in this study is 737. This includes a total enrollment of 652 participants in the CHW Intervention (326 treatment participants and 326 control participants, accounting for 10% attrition), 10 subjects who participate in the provider surveys, 25 participants in the key informant interviews and 50 focus group participants.

CHW Intervention

Inclusion Criteria: Participants will be eligible for study participation if they meet the following criteria: a) are of South Asian ethnicity (identified through a race and language code in the EHR or at screening); b) are at least 21 years of age and younger than age 85, c); d) a diagnosis of diabetes in the EHR or self-reported through community recruitment and e) a diagnosis of hypertension or self-reported diagnosis through community recruitment; f) an uncontrolled BP reading(>130/80mmHg) in the last 6 months or at screening.

Exclusion Criteria: a) Patients under the age of 21 and older than 85 will be excluded. b) Women who are pregnant at the time of screening. c) Type 1 diabetes or diabetes secondary to other conditions (e.g. steroid-induced, pancreatic insufficiency, or chemotherapy-induced), d) inability to perform unsupervised physical activity.

No children will be enrolled in this study.

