Clinic to sign the consent form and complete the baseline survey. Control participants will not be contacted during the intervention and will only be contacted once the intervention with treatment participants has been completed; those who were control in the first wave of recruitment can then be enrolled in the second wave. Due to the study funding period, those in the second wave control arm will be offered education sessions as a point of service and not as part of research.

CHW Intervention Period

There is a 6-month intervention period immediately following recruitment. Each session will be held multiple times throughout the month to accommodate a variety of schedules by the treatment participants. Month 1 has participants coming to Session 1 followed by one follow-up phone call. Month 2 has participants coming to Session 2 followed by one follow-up phone call and then one in person visit at the participant's home or at local meeting point used for a session. Month 3 has participants coming to Session 3 followed by two follow-up phone calls within the month. Month 4 has participants coming to Session 4 followed by one follow-up phone call and then one in person visit at the participant's home or at local meeting point used for a session. Month 5 has participants coming to Session 5 followed by two follow-up phone calls within the month. Month 6 concludes the intervention period with an endpoint survey and completion certificate.

Provider Surveys

Over the course of 2 months, providers at participating practices will be invited to complete the Provider Survey via email link. Paper surveys will also be available for those who prefer to fill out the survey in hard copy. No undue pressure will be given to subjects for participation as the participation is entirely voluntary and will be described via email or verbally to the invited participants (See Invitation Script and Elements of Informed Consent for Provider Survey).

Key Informant Interviews

Over the course of 2 months, participating providers and community health workers will receive an invitation to participate in the interview (See Invitation Script and Elements of Informed Consent for Key Informant Interview). No undue pressure will be given to subjects for participation as the participation is entirely voluntary (See Verbal Consent Script for Key Informant Interview).

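### The comparator is worded two ways, and no sentence keeps a crossed-over first-wave control's later record out of the primary analysis

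*Combined protocol and SAP*

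**What the plan says.** **Comparator by time.** Section III.B1 describes a modified stepped wedge with two groups starting in phases, and states: "The time prior to the intervention will serve as the comparison group". The Aim 2 hypothesis in VII.B1 is also worded by period of care: "Individuals receiving care during the implementation of the intervention will be more likely achieve BP control", set against usual care.

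**Comparator by randomised arm.** The next sentence of III.B1 reads "Enrolled patients will be randomized to treatment (Group A) and wait-list control (Group B) groups within each site". In VII.B1 the indicator H is 1 if the patient was randomised to the CHW intervention and 0 otherwise, and its coefficient is tested against zero. Equation (1) contains an intercept, a fixed effect for clinic site and H, and nothing for period, wave, person or CHW. The power calculation (VII.B2) takes 15% against 35% in two evenly randomised groups.

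**Crossover.** Section VI.A says "those who were control in the first wave of recruitment can then be enrolled in the second wave". VII.A says of controls "Those in the first wave will be offered the intervention in the second wave", whereas second-wave controls get sessions as a service outside the research. III.B1, however, describes all controls as "326 control participants who may receive the CHW intervention as a point of service at a later point".

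**The concern.** A first-wave control who takes up the intervention can have two six-month outcomes, one untreated and one treated. An analyst then has to decide whether the second outcome is used and, if so, under which value of H. The plan does not say whether such people are randomised again, assigned directly to treatment, or counted among the 326 treated. Equation (1) has no term that would handle a second record from the same person or a change between waves.

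Two sentences of the plan define the comparison by time, so a record-level, time-based dataset would not obviously breach it. If the choice is left until outcomes are known, the options give materially different estimates, and at least one of them dilutes a real effect.

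**Working it through.** **1. Which comparison is powered?** Inputs from VII.B2: 15% and 35%, two-sided 5%, 80% power, 1:1, 10% loss. With pooled variance under the null,

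n per arm = [1.96·√(2·0.25·0.75) + 0.842·√(0.15·0.85 + 0.35·0.65)]² / 0.20² = 72.4, so 73 evaluable.

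Multiplying by 1.1 gives 81 per arm, 162 in total, which is the plan's figure. Dividing by 0.9 gives 82 per arm, 164 in total. At 81 × 0.9 = 72.9 evaluable per arm, power is 0.803. The power section is therefore a calculation for two independent randomised arms, not for a before-and-after comparison.

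**2. What the model text settles.** H follows randomisation, so a control who is not randomised again has H = 0. The text describes the control log odds as applying to the first 6 months, which points to the first record. But that phrase is attached to a parameter (μ + b_j) that does not appear in equation (1), and the outcome is written Y_ijk in the text and Y_ij in the equation, with k never defined. It is an indication, not a rule for selecting records.

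**3. Later record replaces the first, kept as H = 0.** From the plan: 326 × 0.9 = 293 evaluable per arm; 15% and 35%. Assumed, because the plan gives no figures: wave 1 holds a share f of participants; a share u of wave-1 controls roll over, from 40% (VII.B3's consent rate for new patients) to 100% (VII.A offers it to all of them); roll-overs reach 35%.

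Control rate = 0.15(1 − uf) + 0.35uf.

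| f | u | Control rate | Difference | Power |
|---|---|---|---|---|
| 1/2 | 0.4 | 19.0% | 16.0 points | 99% |
| 1/2 | 1.0 | 25.0% | 10.0 points | about 75% |
| 2/3 | 1.0 | 28.3% | 6.7 points | 41% |

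With first records only, the difference is 20 points and power exceeds 99.9%.

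If both records are pooled under H = 0, the control rate is (0.15 + 0.35uf)/(1 + uf). With f = 1/2 the difference is 16.7 points at u = 0.4 and 13.3 at u = 1.

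**4. Later record pooled as H = 1, no true effect.** This adds a non-randomised group to the treated arm and treats two records of one person as independent. The bias depends on how untreated control changes over time:

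- Suppose a share s of controlled people stay controlled and uncontrolled people have a fresh 15% chance. The roll-over rate is then 0.15s + 0.85·0.15, and the treated rate is (0.15 + rate·uf)/(1 + uf). With f = 1/2, u = 0.4, s = 0.5 the rate is 20.25% and the bias +0.9 points. With u = 1, s = 0.9 the rate is 26.25% and the bias about +3.8 points.
- Under plain regression to the mean (stable personal level, visit correlation 0.5 to 0.8, simulated), untreated control is again 15% at month 12 and the bias is about 0.
- Under that same model, if only people still uncontrolled re-enter (equal waves, full roll-over), the bias is about −1.1 to −1.8 points.

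The plan does not say whether roll-overs are re-screened, and the entry criterion accepts "an uncontrolled BP reading(>130/80mmHg) in the last 6 months or at screening", so none of these can be ruled out.

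**5. Shared CHW (separate point).** VII.B3 gives a caseload of about 16. The intraclass correlation (ICC) is assumed to be 0.02 to 0.05. Treated-arm design effect = 1 + 15·ICC = 1.30 to 1.75. At equal rates the variance of the difference is inflated by (1.30 + 1)/2 = 1.15 to (1.75 + 1)/2 = 1.375. A nominal 5% test then has size 2[1 − Φ(1.96/√1.15)] = 6.8% to 2[1 − Φ(1.96/√1.375)] = 9.5%. At 293 per arm, power for 35% against 15% stays above 99%.

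**The case against.** The best reply is that the plan already does the right thing. H is fixed by randomisation, the outcome is taken at the end of six months, and the control reference is the first six months. III.B1 opens by calling the design randomised and VII.A calls it wait-listed, so the disputed sentence may mean only Group B's waiting time, which is a concurrent control period. Most of this stands. Claiming that the plan gives no indication of arm or record would be too strong. What remains is that no sentence excludes the later record and the status of roll-overs in wave 2 is not stated.

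Three stronger inferences are tempting and not supported:

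- **Each person is compared with their own earlier time**, so that regression to the mean counts as benefit. The written model does not make that comparison.
- **Repeat records are certainly planned for the primary analysis**, because "patients who are observed more than once will have the same study ID in each extract, which is necessary for the planned analyses". That sentence stands under treatment participants and is followed by a statement that data are collected at baseline and endpoint, which may be all it means.
- **Pooling roll-overs as treated manufactures an effect.** That holds only if untreated control rises over time. VII.B2 reports almost no change among past controls, and the qualifying wave-1 reading would usually be more than six months old by wave 2.

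**Conclusion.** The concern holds in a limited form. The comparator wording in III.B1 and in the Aim 2 hypothesis does not match the randomised comparison that is modelled and powered, and the plan lacks a rule excluding a crossed-over control's second-wave record. Applied to each person's first randomised period, the planned comparison is unbiased.

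The dilution figures (16 to 10 points with equal waves; 6.7 points if wave 1 holds two thirds and everyone rolls over) rest on assumed wave shares and uptake, on roll-overs reaching 35%, and on an analyst setting aside the first-six-months phrase. For pooling as treated, neither the size nor the sign can be given from the documents. The CHW point is independent of these and rests on an assumed ICC. Severity: minor to should-fix.

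**What to change.** 1. In III.B1, replace the comparator sentence with: *Concurrent participants randomised to wait-list control are the comparison group.* Reword the Aim 2 hypothesis to compare participants randomised to the CHW intervention with those randomised to control.
2. In VII.B1, add: *The primary analysis compares arms as randomised, using each unique participant's first randomised six-month period only; records after a control crosses over are not used.* Allow roll-over records only in a secondary analysis with a period term, time-varying exposure and person-level clustering.
3. Reconcile III.B1, VI.A and VII.A on whether first-wave controls receive the later intervention as research or as a service, and say whether they are randomised again or count toward the 326 treated. Reconcile VII.B3, which has 652 people enrolled every six months and controls matched to treated patients, with the total of 652 randomised in III.B1 and V.A.
4. Separately, because treated patients share a CHW and group sessions, add a treated-arm CHW random effect or a cluster-robust standard error with small-sample correction to model (1).

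The cost is a few sentences and one variance term; the randomised comparison does not change. Roll-over records no longer add to the primary count. For the assumed ICCs the confidence interval widens by about 7% to 17% at equal rates (√1.15 = 1.07, √1.375 = 1.17).
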